1.3 Duration of the Investigation

Enrollment for the study is expected to take 12 months.

Subjects will be on study prior to their radiation treatment simulation (approximately 1-2 weeks), during their radiation treatment simulation, plan selection, and delivery (≤ 7 business days), and during post-treatment follow-up (until subject death or lost to follow-up). In general, subjects with metastatic disease have a guarded prognosis. Their survival varies with their diagnosis and rate of disease progression. Thus, it is not possible to specify the duration of a subject's participation in the study. Subject participation may last from a few months to several years.

The study may run from 1.5 years to several years (which covers enrollment, treatment, follow-up, and completion of data analyses).

2 Protocol

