The effects of FLASH radiotherapy have been studied in vitro and in animals with encouraging results. Compared to radiotherapy given at conventional dose rates, FLASH radiotherapy has been shown in multiple models to cause less injury to normal cells and tissue, while having equal or greater tumor cell killing. Favaudon et al. irradiated mouse lungs *in vivo* with both FLASH radiotherapy and conventional dose rate radiotherapy (CRT) [1]. Using a single dose of 17 Gy, 100% of mice given CRT developed pneumonitis and fibrosis whereas none of the mice given FLASH radiotherapy developed these toxicities. FLASH radiotherapy doses were escalated to 30 Gy single dose before the mice began developing pneumonitis and fibrosis. The same investigators treated orthotopic lung tumors in mice with single dose FLASH radiotherapy and CRT. 15 Gy CRT controlled tumors in only 20% of mice, most of which developed significant pneumonitis. 27 Gy FLASH radiotherapy controlled tumors in 70% of mice, none of which developed pneumonitis.

Montay-Gruel et al. treated mouse brains *in vivo* with 10 Gy of radiation using both FLASH radiotherapy and CRT techniques. Neurocognitive impairment developed subsequently in the CRT group whereas mice treated with FLASH radiotherapy remained functionally intact [2]. The normal tissue sparing effects of FLASH have also been observed in several other tissues and animal models including mouse intestine [3], mouse skin [4], and cat and pig skin [5]. The mechanism for FLASH is not fully understood, but there are data that suggest FLASH produces lower levels of toxic oxygen reactive species in normal tissues as compared to CRT [6].

To date, there has been one published case report of the use of FLASH radiotherapy in a human. A single patient with cutaneous T cell lymphoma and extensive prior radiotherapy to the skin was treated with electron FLASH radiotherapy for a recurrent cutaneous lymphoma lesion. A

single dose of FLASH radiotherapy using 15 Gy electron radiotherapy was delivered. This resulted in a complete response of the lesion with minimal toxicity to the surrounding skin [7].

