2.8.7 Adverse Event Checks

Adverse events will be monitored from start of treatment to completion of the final study follow-up visit. Adverse event checks will take place on the day of treatment (Day 1 after treatment delivery) and at the follow-up visit time points Day 15, Month 1, Month 2, Month 3, and long-term follow-up (see section 2.2.2 Schedule of Activities table). The adverse event check on Day 2 will be carried out by remote review. All other adverse event checks during follow-up may be carried out using a combination of remote visits and/or records review as an alternative to in-person visits to accommodate the subject's inability or reluctance to travel. Adverse event checks will be recorded on the corresponding case report form. All adverse events will be collected regardless of severity or attribution. Adverse events will be classified per CTCAE version 5.0.

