2.13 Planned Analyses, Sample Size, and Stopping Rules

The Sponsor will conduct the following analyses corresponding to the study objectives and prepare a clinical study report. Where appropriate, descriptive statistics will be used.

Primary Objective:

1. Workflow feasibility:

For each subject, workflow feasibility will be judged as successful or not based on the following criteria:

Treatment for an individual subject will be deemed NOT feasible if:

- Total treatment time on table is greater than one hour OR
- A delay in study treatment of more than 7 business days from simulation to treatment occurs related to the investigational device (excluding delays due to patient or facility factors not related to the study treatment)

2. Toxicities of treatment:

All toxicities will be tabulated and summarized. Toxicities that are possibly, probably, or definitely related to FLASH radiotherapy will be used for the assessment of toxicity of the FLASH treatment.

Note: A dose-limiting toxicity (DLT) is defined as a Grade ≥ 3 toxicity attributed as possibly, probably, or definitely related to FLASH radiotherapy. The number of DLTs will be monitored through the duration of the study and will be used as a criterion in the Stopping Rules (see section 2.13 for a Stopping Rule related to DLT.)

Secondary Objective:

3. Pain relief:

As discussed above in section 2.8.6 patient reported pain score (overall) at baseline and post-treatment (Day 15, Month 1, Month 2, Month 3, long-term) will be assessed using the Brief Pain Inventory (BPI) short form questionnaire. Patient reported pain score for each treated site will be assessed using the Treated Sites Pain questionnaire.

The BPI short form questionnaire was selected to permit the results of this study to be compared with prior published results using this instrument [10].

Per the methodology of Hartsell, et al. [10]: The worst pain score in the BPI short form will be used to assess treatment response; a complete response will be defined as having no pain at 3 months after radiation therapy; a partial response will be defined as a pain score that is at least two points lower than the initial response; a stable response

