will be defined as a one-point change in pain score in either direction; a progressive response will be defined as a pain score that is at least two points higher than the initial score. The same analysis will be applied to the individual sites treated by FLASH, as assessed by the questionnaire with the four-item subset of the BPI questionnaire.

Per the methodology of Chow et al., flare in bone pain due to radiation will be assessed using the Pain Flare questionnaire administered on Day 1 - Day 11. Pain flare is defined as either of the following: a minimum of a two-point increase in the worst pain score for the treated site without a reduction in analgesic intake; or a 25% or greater increase in analgesic intake based on daily oral morphine equivalence without a reduction in the worst pain score. If the worst pain score before treatment was nine or ten, the criteria for pain flare were met if the follow-up worst pain score was ten and reported as worse than the worst pain before treatment with no decrease in analgesic intake. To distinguish pain flare from progression of pain, the worst pain score and analgesic intake had to return to baseline levels during the 11-day (Day 1 - Day 11) time period. Consistent with the Chow study, we will document use of steroid medication.

Data on use of pain medication will be collected and changes in pain medication use will be evaluated between baseline, during each of the first 10 days after treatment, and follow-up visits (Day 15, Month 1, Month 2, Month 3). The percentage of patients requiring narcotic, non-narcotic analgesics, and no pain medications will be assessed and compared to literature values from prior clinical trials.

Sample Size:

For this feasibility study, a sample size of up to 10 patients will apply.

Stopping Rules:

Triggering of a stopping rule will result in a cessation of enrollment and in a review of the study data by the Cincinnati Cancer and Blood Disease Institute Data Safety Monitoring Board and Study Committee (PI and co-investigators).

The study will be stopped if any of the following occurs:

- 3 subjects experience a dose limiting toxicity (DLT) (see section 2.13 for definition of DLT)
- 3 subjects have time on the treatment table >1 hour
- 3 subjects have a delay in study treatment of more than 7 business days from simulation to treatment related to the investigational device (excluding delays due to patient or facility factors not related to the study treatment.)

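### The DLT stopping rule can protect only subjects not yet treated, and nothing in the plan ensures that one subject's early adverse event evaluation is known before the next is treated

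*Combined protocol and SAP*

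**What the plan says.** Section 2.13 defines a DLT as a Grade 3 or higher toxicity at least possibly related to FLASH radiotherapy. It sets no time window: "The number of DLTs will be monitored through the duration of the study and will be used as a criterion in the Stopping Rules". Three subjects with a DLT trigger the rule.

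The consequence is worded in two ways. One sentence reads "Triggering of a stopping rule will result in a cessation of enrollment and in a review of the study data", the review being by the data safety monitoring board (DSMB) and the study committee. The next reads "The study will be stopped if any of the following occurs".

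Under section 2.8.7, adverse events are checked on the day of treatment and "at the follow-up visit time points Day 15, Month 1, Month 2, Month 3, and long-term follow-up", with a remote check on Day 2. In the Schedule of Activities (2.2.2) the first physical evaluation after treatment, with skin photographs, is at Day 15. Section 2.9 requires serious adverse events to reach the Sponsor within 24 hours of the investigator learning of them.

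On pace, section 1.3 says only "Enrollment for the study is expected to take 12 months". Section 2.6 gives one site, and section 2.13 allows up to 10 patients. The available text has no minimum interval, no cohorts, no hold for a previous subject's check and no limit per day or week. On earlier human experience, section 2.3 says "To date, there has been one published case report of the use of FLASH radiotherapy in a human"; that patient was treated with electrons.

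**The concern.** All study radiation is given on Day 1, so neither stopping enrolment nor stopping the study changes the exposure of anyone already treated. The rule works only as far as earlier outcomes are known when the next subject comes to treatment, and the plan leaves that to chance.

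This matters more than usual here. Toxicity is a primary objective, the modified device delivers protons rather than the electrons of the one cited human case, and section 2.9 expects most toxicity to be in the skin, which is not physically examined again until Day 15. What is at stake is additional subjects treated while the DLT count is incomplete.

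**Working it through.** **Inputs from the documents.** Up to 10 treated subjects and a threshold of 3 DLT subjects (2.13); 12 months expected enrolment (1.3); Day 15 falls 14 days after Day 1 (2.2.2, 2.8.8). The plan gives no operating characteristic for the rule, so there is no figure of its own to reproduce.

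**Assumptions.** Random (Poisson) arrivals; true DLT rate 10%, 30% or 50%; each DLT known a fixed 14, 30 or 90 days after treatment; accrual over 12 months, with 6 and 3 months as alternatives. Results with a detection lag come from simulation.

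**1. How often the rule is met.** P(X ≥ 3) with X ~ Binomial(10, p) is 7.0%, 61.7% and 94.5% at p = 0.1, 0.3 and 0.5.

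**2. How often treatments fall too close together.** The mean gap is 365/10 = 36.5 days.
- P(gap < 14) = 1 − exp(−14/36.5) = 0.319, or 9 × 0.319 = 2.9 of the 9 gaps.
- P(at least one of 9) = 1 − 0.681^9 = 0.968.
- With accrual over 6 or 3 months (mean gap 18.25 or 9.125 days), 53.6% or 78.4% of gaps are under 14 days.

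**3. Extra subjects treated.** If every outcome is known before the next treatment, the mean number treated is the sum over k = 0 to 9 of P(Binomial(k, p) ≤ 2). That is 8.13 at p = 0.3 and 9.85 at p = 0.1. Without a hold, and with DLTs known at Day 15, simulation gives:
- p = 0.3, 12 months: 8.34, an excess of about 0.2;
- p = 0.3, 3 months: 8.87, an excess of about 0.7;
- p = 0.1, 12 months: 9.87, an excess of about 0.02.

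Per trigger at p = 0.3:

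| Accrual | Extra subjects per trigger | Triggers coming only after all 10 are treated |
|---|---|---|
| 12 months | 0.32 | 19% |
| 6 months | 0.63 | 24% |
| 3 months | 1.16 | 36% |

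The two scales agree: 0.617 × 0.32 = 0.20 and 0.617 × 1.16 = 0.72. In the last column, 13% is unavoidable, because the third DLT may fall on subject 10: 36 × 0.3^3 × 0.7^7 / 0.617 = 0.080/0.617 = 0.13. Holding every gap past Day 15 removes the excess and returns that column to 13%.

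**4. Later DLTs (p = 0.3, 12 months).** With a 30-day lag the excess per trigger is 0.67 without the hold and 0.68 with it. With a 90-day lag it is about 1.7 either way. A Day 15 hold does not help with these.

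**5. Holding only the first subjects.** With a 50% DLT rate, 12-month accrual and Day 15 detection, holding only the first two or three gaps leaves the mean number treated at 6.20 to 6.22, against 6.22 with no hold. With 3-month accrual and a 30-day lag it rises from 8.4 to 8.7–9.0 when subjects who waited are then treated close together. The rule needs three DLTs, so what matters is the spacing after subject 3.

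**6. Expected wait.** For a hold of h days the wait per gap is h − 36.5 × [1 − exp(−h/36.5)].
- h = 14: 14 − 36.5 × 0.319 = 2.4 days.
- h = 15 (treatment the day after the evaluation): 15 − 36.5 × 0.337 = 2.7 days, and 9 × 2.7 = 24 days.
- Longer gaps absorb part of this, and simulated accrual stays at about 12.2 months. Ten treatments 15 days apart span at least 9 × 15 = 135 days.

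**The case against.** The strongest reply is that the gap hardly matters in practice. One site expecting 10 subjects in 12 months averages 36.5 days between treatments, well beyond 14. Day 1 and Day 2 checks, 24-hour notification of serious events, and a Sponsor medical monitor (section 5) mean that a severe early event need not wait for Day 15. The benchmark trial described in section 2.9 had no acute Grade 3 or 4 skin toxicity among 433 patients given the same single 8 Gy fraction at standard dose rate, so a 30% DLT rate is pessimistic. Day 15 is also a somewhat arbitrary hold point when the DLT has no time window and the benchmark's acute window is 90 days.

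Most of this stands as an argument about size, and it is why the expected excess is a fraction of a subject. It does not close the gap. The safeguards report events once they are known; none makes the next treatment wait. Serious events are defined by outcome and DLTs by grade, so a Grade 3 skin reaction managed as an outpatient may be a DLT without prompting 24-hour notice. The benchmark rate is for conventional dose rate, and FLASH toxicity is what this study sets out to measure.

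A reader might infer that the trigger will come too late to spare anyone. The text permits that but does not make it likely: the chance that subjects 4 to 10 are all treated within 14 days of subject 3 is about 2 in 10 million at the stated pace and 0.1% if accrual takes 3 months. A reader might also infer that the DLT count is the only toxicity safeguard, which the checks and notification above contradict.

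**Conclusion.** The omission is real and its expected effect at the planned pace is small. Short gaps are near certain (about 97% for at least one), but they cost on average about 0.2 extra subject at an assumed 30% DLT rate (about 0.3 per trigger), close to nothing at 10%, and about 0.7 if accrual takes 3 months. All 10 being treated before the rule can act is a permitted extreme, not the expected course. These figures rest on assumed random arrivals, DLT rates and a fixed detection time, none of which the documents supply. Pages removed from the public version could not be checked. This is a cheap safety improvement, not a flaw that undermines the study.

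**What to change.** Add one trial-conduct sentence to the Stopping Rules in 2.13: for every subject, not only the first three, the next subject is not treated until the previous subject's scheduled early adverse event evaluation is recorded and the DLT count updated. The evaluation can be Day 15, or another visit already in the Schedule chosen by the Sponsor and the DSMB. Simulation should be timed so that the hold falls before it and the window of 7 business days from simulation to treatment is kept.

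State beside it that a Day 15 hold does not cover later DLTs.

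In the same edit, reconcile the two wordings of the consequence, enrolment ceasing and the study being stopped, so that it is clear what happens to subjects enrolled but not yet treated.

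The cost is one sentence, with no new visit and no change to any subject's treatment. The expected wait is 2 to 3 days per gap and about 24 days in total at the stated pace. It is longer if accrual is faster: at 3 months, 15 − 9.125 × 0.807 = 7.6 days per gap, or about 69 days over nine gaps. A subject who cannot wait would be treated off study.

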Grades will be assigned to clinical AEs by the investigator or his/her designee per the CTCAE version 5.0, which consists of a scale from 1 to 5 to describe the severity of the AE. A copy of the CTCAE version 5.0 will be provided. For reference, an overview of the grades is given below, but the CTCAE v5 needs to be consulted for specific grading criteria:

- Grade 1 – Mild, asymptomatic or mild symptoms; clinical or diagnostic observations only; intervention not indicated.
- Grade 2 – Moderate; minimal, local or noninvasive intervention indicated; limited age-appropriate instrumental activities of daily living (ADL). Instrumental ADL refer to preparing meals, shopping for groceries or clothes, using the telephone, managing money, etc.
- Grade 3 – Severe or medically significant but not immediately life-threatening; hospitalization or prolongation of hospitalization indicated; disabling; limiting self-care ADL. Self-care ADL refer to bathing, dressing and undressing, feeding self, using the toilet, taking medications, and not bedridden.

- Grade 4 – Life-threatening consequences; urgent intervention indicated.
- Grade 5 – Death related to AE.

There are anticipated adverse events associated with the delivery of 8 Gy radiation in a single fraction at standard dose rate for the treatment of bone metastases. The frequency and severity of these toxicities were evaluated at standard dose rates in a prior benchmark multi-institutional prospective randomized clinical trial [10]. In this trial, a cohort of 455 patients (433 and 354 patients analyzed for acute and late toxicities, respectively) were treated with 8 Gy for palliation of painful bone metastases. Grade 2-3 acute toxicity (within 90 days after starting radiation therapy) occurred in 10% of the patients, and “late toxicity was rare (4%)”. The most common toxicity was gastrointestinal, which accounted for approximately half of all acute adverse events. Gastrointestinal toxicity should not be relevant to the present feasibility study as treatment is limited to the extremities. No patients in the cited study receiving 8 Gy had Grade 4 acute or late toxicities.

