- A major device malfunction in dose delivery (as indicated by the dose monitoring system). This includes potential recordable or reportable medical events under the Ohio Department of Health classification.

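### Section 2.13 pools related Grade 3, 4 and 5 toxicities in one three-subject DLT trigger, so one or two subjects with related Grade 4–5 events do not by themselves prompt an enrolment hold or DSMB review under that section

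*Combined protocol and SAP*

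**What the plan says.** Section 2.13 defines the event that is counted: "A dose-limiting toxicity (DLT) is defined as a Grade ≥ 3 toxicity attributed as possibly, probably, or definitely related to FLASH radiotherapy". The grading summary in section 2.9 describes Grade 4 as life-threatening and ends with "Grade 5 – Death related to AE". The DLT class therefore runs from severe to fatal without subdivision.

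The Stopping Rules in 2.13 list four triggers:

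- One concerns toxicity: "3 subjects experience a dose limiting toxicity (DLT".
- Two concern workflow, and each needs three subjects (table time over one hour; device-related delay of more than 7 business days).
- One can be met by a single occurrence: "A major device malfunction in dose delivery (as indicated by the dose monitoring system". It extends to potential recordable or reportable events under a state health department classification.

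The consequence is common to all four: "Triggering of a stopping rule will result in a cessation of enrollment and in a review of the study data", with the review done by a named DSMB and the Study Committee. The sample size is up to 10.

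On prior human experience, section 2.3 says "To date, there has been one published case report of the use of FLASH radiotherapy in a human". For the benchmark trial of 8 Gy at standard dose rate, section 2.9 gives "433 and 354 patients analyzed for acute and late toxicities, respectively" and adds "No patients in the cited study receiving 8 Gy had Grade 4 acute or late toxicities".

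**The concern.** A related death after a correctly delivered dose counts exactly as one Grade 3 event does: one subject of the three needed. A second such death still leaves the count at two. The single-occurrence trigger is defined by a fault in delivery, not by harm to a subject. One malfunction stops enrolment whether or not anyone is injured, while one or two related life-threatening or fatal toxicities without a malfunction do not.

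This matters because the plan has little human experience to draw on. Section 3.2 expects normal tissue toxicity to be no greater than with conventional photon treatment, and the benchmark reported no Grade 4 toxicity. A related Grade 4 or 5 event would contradict that expectation, and it is the kind of event after which independent review before the next subject is most useful. As written, 2.13 leaves that review to discretion until a third subject has a DLT.

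**Working it through.** **Reading the rules together.** Take a subject with a related Grade 4 or 5 event, correct delivery, table time under one hour and no device-related delay. The DLT count rises by one, and neither the workflow triggers nor the malfunction trigger applies. With two such subjects and no other DLT, the count is two and no trigger is met. The events are not ignored: one further subject with any DLT, Grade 3 included, would complete the three.

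**Plan's own figure.** There is none to reproduce. The documents give no operating characteristics for the three-subject threshold and no derivation of the sample size.

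**Inputs.** n = 10 and threshold 3 (section 2.13). Benchmark Grade 4 events: 0 of 433 analysed for acute toxicity and 0 of 354 for late toxicity (section 2.9). The documents give no FLASH rate, so every per-subject rate r below is an assumption.

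**Benchmark bounds.** With zero events in m patients, the one-sided 95% upper bound is 1 − 0.05^(1/m).

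- Acute: 1 − 0.05^(1/433) = 0.0069
- Late: 1 − 0.05^(1/354) = 0.0084
- Summed: 0.0069 + 0.0084 = 0.0153

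**Binomial probabilities, n = 10.** X is the number of subjects with a related Grade 4–5 event.

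- P(X ≥ 1) = 1 − (1 − r)^10
- P(X ≥ 2) = 1 − (1 − r)^10 − 10r(1 − r)^9
- P(X = 1 or 2) = P(X ≥ 1) − P(X ≥ 3). This is the chance of such events with no DLT trigger if they are the only DLTs.

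| Assumed r | P(X ≥ 1) | P(X ≥ 2) | P(X ≥ 3) | P(X = 1 or 2) |
|---|---|---|---|---|
| 0.69% (acute bound) | 6.7% | 0.2% | <0.1% | 6.7% |
| 0.84% (late bound) | 8.1% | 0.3% | <0.1% | 8.1% |
| 1.53% (summed) | 14.3% | 1.0% | <0.1% | 14.3% |
| 5% (illustration) | 40.1% | 8.6% | 1.2% | 39.0% |
| 10% (illustration) | 65.1% | 26.4% | 7.0% | 58.1% |

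At the acute bound, two such subjects would be strong evidence against the benchmark (probability about 0.2%), yet they would not meet the rule.

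**Allowing for Grade 3 DLTs.** Suppose a further g = 10% of subjects have a related Grade 3 DLT only, and let q = r + g. The chance of at least one Grade 4–5 subject with fewer than three DLT subjects is the sum over k = 1, 2 of C(10,k) q^k (1 − q)^(10−k) [1 − (g/q)^k].

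- r = 5%: 0.347 × 1/3 + 0.276 × 5/9 = 0.269
- r = 10%: 0.268 × 1/2 + 0.302 × 3/4 = 0.361

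The gap narrows from 39% and 58% to 27% and 36%.

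**When a hold can still act.** Enrolment cannot be held after the tenth subject. Over the first nine subjects, with no other DLTs, a single-event rule fires with probability 1 − 0.95^9 = 37% and 1 − 0.90^9 = 61% at r = 5% and 10%. The three-DLT rule fires in 0.8% and 5%.

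**The case against.** **The threshold was considered.** The revision history records that it was changed to at least three subjects after scientific review committee feedback, and that the stopping rules were revised again later. FDA and IRB review precede enrolment. This stands as evidence that the count was deliberate. It does not show that pooling Grade 4 and 5 with Grade 3 was considered.

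**Other oversight exists.** A reader might infer that nothing happens after a related death. The documents do not support that. SAEs reach the sponsor within 24 hours, reportable events go to the IRB, and UADEs are reported and evaluated under 21 CFR Part 812. A Grade 4 or 5 event may well qualify as a UADE on severity, since that definition covers effects not previously identified in severity. DLTs are monitored throughout, there is a medical monitor, and the sponsor can terminate the study. All of this stands. None of these routes is tied to a mandatory hold or DSMB review in the available text.

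**Some text could not be checked.** Material between the opening of section 5 and the later part of section 9 was not available, and the state classification named in the malfunction trigger is not reproduced. An equivalent provision elsewhere cannot be excluded, so the point is confined to 2.13.

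**The large percentages come from assumed rates.** This is correct. Rates of 5% and 10% lie about 7 and 14 times above the acute bound (5/0.69 and 10/0.69). A reader might take 39% and 58% as forecasts; the documents give no basis for that. Within the bounds, two or more such subjects occur in at most about 1% of studies, and the 7–14% chance of at least one event is also the chance of a review that proves unnecessary. The case rests on the gravity of the event, not on a claim that it is likely.

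**Conclusion.** The point holds for section 2.13 as written: one or two subjects with related Grade 4–5 events after correct delivery do not by themselves trigger an enrolment hold or DSMB review. It is a design choice that can be improved cheaply, not a contradiction or a miscalculation.

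The text alone establishes the gap. Its practical size depends on an unknown rate. At the benchmark's acute bound, two or more such subjects would arise in about 0.2% of studies and leave the rule unmet. At 5% and 10%, one or two such subjects with no trigger would arise in 39% and 58% if these are the only DLTs.

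The figures assume 10 independent subjects with a common rate. The bounds come from a trial at standard dose rate, scored on RTOG criteria rather than CTCAE. They rest on Grade 4 counts only, because section 2.9 gives no Grade 5 count. Confidence is medium, given the unavailable text. The stronger readings, that the plan lacks safety oversight or that such events are expected, are not supported.

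**What to change.** Keep the three-subject DLT rule. Add one sentence to the Stopping Rules in 2.13: any single Grade 4 or 5 event carrying one of the three attributions that count toward a DLT leads to a pause in enrolment and review by the DSMB already named there. If an equivalent rule exists in another section or document, cite it in 2.13 instead. The change concerns study-level enrolment and oversight only, and leaves each subject's dose and treatment untouched.

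The drafting cost is one sentence. The operating cost is an occasional review that proves unnecessary during a planned 12-month enrolment: about 7% of studies at the acute bound, 8% at the late bound and 14% at their sum. These are not ceilings. Section 2.9 lets an event be rated possibly related when another cause may explain it, which could raise the number of reviews in patients with metastatic disease.
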